Study Protocol

Change in Body Weight During Treatment of Advanced Colorectal Cancer

PROTOCOL DATE: January 1, 2019

PROPOSED RESEARCH PROJECT

- a) Title:
Change in Body Weight During Treatment of Advanced Colorectal Cancer

Abstract

Objectives: To evaluate whether change in body weight in advanced colorectal cancer patients occurring during systemic anti-cancer treatment influences treatment outcomes

Hypothesis to be tested: Weight loss during treatment is associated with adverse treatment outcomes in patients with advanced colorectal cancer, compared to patients without weight loss or with weight gain.

Design: A pilot, prospective, single-centered observational study of patients with advanced colorectal cancer having first line systemic anti-cancer treatment.

Setting: Outpatient Clinical Oncology clinic in Tuen Mun Hospital

Participants: Patients having histologically proven stage IV colorectal adenocarcinoma, requiring systemic anti-cancer treatment, which entail chemotherapy (5-fluouracil, capecitabine, oxaliplatin and irinotecan) with or without targeted therapy (cetuximab or bevacizumab) as first line treatment.

Main outcome measures: Primary outcomes: disease control rate, progression free survival. Secondary outcomes: Dose reduction of systemic chemotherapy.

- b) Introduction:

Colorectal cancer (CRC) is a significant and growing health burden in Hong Kong. According to data from Hong Kong Cancer Registry, CRC ranked the first in incidence and the second in mortality, with around 5,000 new cases diagnosed and more than 2,000 cancer-related mortality in 2014.¹ Around one-fourth of CRC present as metastatic disease; it is also estimated that 50-60% of patients diagnosed with CRC eventually develop metastasis during their course of disease.² Among metastatic CRC (mCRC) patients, only few with limited metastases are potential long-term survivors after receiving locoregional treatment,³ while the majority of them are incurable and the standard treatment is systemic therapy.

Over the past 15 years, the introduction of molecular targeted therapy into mCRC treatment armamentarium has dramatically improved the prognosis, with the median overall survival (OS) 14-16 months in the pre-targeted therapy era compared with around 30 months nowadays.⁴ Systemic therapy with combination chemotherapy, Oxaliplatin-based or Irinotecan-based, plus targeted therapy, either anti-epidermal growth factor receptor (anti-EGFR) monoclonal antibody (mAb) or anti-vascular endothelial growth factor (anti-VEGF) mAb becomes the current standard first-line treatment.

Studies have suggested that exposure to a greater number of chemotherapeutic agents is associated with better survival.⁵ Therefore, the current principle of management of mCRC emphasizes on maximizing the exposure of various chemotherapeutic and molecular targeted agents in a stepwise manner.^{6,7}

However, these treatments have their peculiar side effects. Many chemotherapy treatments are dosed based on body weight or body surface area (BSA), with recommended milligrams (mg) per BSA (m^2) derived from studies testing for dose-limiting toxicities. Nevertheless, many patients still experience severe toxicity and subsequently experience reductions in dose or dose delays or discontinue treatment prematurely.^{8, 9} Discontinuation, reductions, and delays in chemotherapy might adversely affect prognosis by reducing the exposure to therapeutic agents.^{8, 10, 11} Great variability exists in patients' tolerance for cancer treatment that is not explained by age and comorbidities.^{12, 13} Body composition, the amount and distribution of fat and lean soft tissue (the main compartment of which is skeletal muscle mass), is one factor influencing the pharmacokinetics and pharmacodynamics of many chemotherapeutic agents.¹⁴

Studies were conducted to evaluate the role of muscle mass and treatment tolerance and outcome in CRC patients.^{8, 11} Computed tomography (CT) based cross-sectional measurement of muscle mass was shown to be highly correlated with total body muscle mass.¹⁵ Based on this information, in a recent study by Feliciano et al.,⁸ muscle mass was quantified using CT and was used to evaluate if body composition at diagnosis was associated with chemotherapy tolerance and overall survival in the adjuvant setting. The authors concluded that low muscle mass was associated with greater treatment toxicity and poorer chemotherapy adherence.⁸ The evidence so far suggested muscle mass has prognostic value. However, the measurement required specialized software and staff training, making this resource draining and time-consuming. This produces practical difficulty especially for community oncology centers where budget and manpower is tight. It is likely that the measurement will be used mainly as research tool unless computer automation is available widely. Furthermore, other observational studies of muscle mass and treatment outcomes have been limited by modest sample size, and inadequate adjustment for confounding factors such as age, disease stage, race or comorbidities.^{16, 17}

An alternative is to measure the weight change or body mass index (BMI). In patients with CRC weight loss is common at disease presentation.^{9, 10} Weight loss is one of the diagnostic criteria for cancer cachexia, and is closely related to poor prognosis in cancer.¹⁸ Weight loss is not only a problem at diagnosis, but is also encountered during treatment which might impair patients' tolerance to treatment, and treatment outcomes. In one retrospective study, 35% patients with mCRC already had weight loss on presentation, and it was shown that these patients received less systemic treatment on average, had significantly reduced tumor response, failure free survival, and OS.¹⁰ In contrast, weight stabilization or reversal of weight loss during treatment was associated with longer failure free and OS in that study.¹⁰ Similar relationship between serial body weight and outcome has been detected in advanced non-small cell lung cancer patients. Patel et al. reported weight gain of at least 5% was associated with higher response rate (odds ratio 2.55) and overall survival (OS) (HR 0.54), and progression-free survival (PFS) (HR 0.59).¹⁹ Hypotheses include better nutritional status can improve the host's immunity and anti-cancer effects, and tumour control might inhibit or reverse the processes that promote cachexia and allow weight gain.^{19, 20}

Multiple factors might affect body weight during treatment. Cancer-related symptoms can impair quality of life and appetite. Cachexia syndrome affects around 50% of colon cancer patients and is characterized by cancer-induced catabolism with involuntary weight loss (fat and muscle), patients have increased lipolysis and change in skeletal muscle metabolism, including increased energy expenditure at rest and protein degradation, and decreased protein synthesis.²¹ Besides these disease factors, treatment related side effects are common causes of weight loss, such as inability to ingest or digest food effectively due to nausea, vomiting, and malaise. Based on these factors and the hypotheses between tumour control and weight gain, monitoring the serial weight change can have practical value. Body weight can be monitored readily in each clinical follow-up session. Increasing or maintained weight might indicate that the cancer is not worsening and the patient tolerates treatment well. In contrast, weight loss during treatment might alert clinicians to review for disease progression and patient's tolerance to treatment, with corresponding change in strategies initiated (including proactive symptom control, early stopping of ineffective treatment, change in treatment regimen, or earlier palliative care). Cost in healthcare may be saved by more efficient use of resource.²²

As for dose reduction, toxicity, especially hematological, is the most common reason. In patients with metastatic disease, chemotherapy dose intensity is consistently associated with increased rates of complete and partial response, as well as PFS.²³

(1) Primary endpoint: DCR which includes stable disease, partial response and complete response as defined in RECIST 1.1; and PFS defined as the time from randomization until first evidence of objective tumour progression (as defined in RECIST 1.1) or death from any cause, with censoring of patients who are lost to follow-up.

(2) Secondary endpoints: Dose reduction is defined as <70% of relative dose intensity, which represents the ratio of dose intensity (dose given per unit body surface area per unit time i.e. mg/m²/week) actually administered, to standard dose intensity.⁸

d) Plan of Investigation:

(i) Subjects

Sample size calculation:

We used power analysis program G*Power to calculate sample size.²⁴ Estimated proportion of subjects having significant weight loss is approximately 15%. Risk ratio of dose reduction was about 3.0 for patients with significant weight loss, according to a study in adjuvant setting. Prior study indicated that the failure rate among controls is 0.2. We will need to recruit 240 patients to be able to reject the null hypothesis that the primary endpoints (incidence of dose reduction) for patient with and without significant weight loss are equal with probability (power) 0.8. Assuming 10% loss to follow-up, total number of patients to require is 264. The Type I error probability associated with this test of this null hypothesis is 0.05. We will use logistic regression to evaluate this null hypothesis.

Inclusion criteria for studies

We recruit male and female patients aged 18 years or older with stage IV, histologically

confirmed colorectal adenocarcinoma who will receive systemic treatment, an Eastern Cooperative Oncology Group (ECOG) performance status of 0–2, an estimated life expectancy of greater than 3 months, and adequate organ function. We exclude patients who are pregnant, have human immunodeficiency virus infection and acquired immune deficiency syndrome (HIV/AIDS), and past medical history of another cancer.

(ii) Methods

This study is prospective observational cohort study, recruitment period is 24 months. We start to collect data once patient is recruited and individual data can be available before end of recruitment period. Baseline weight (in kilogram), height (in centimeter), and BMI (in kilogram per height in meters squared) are measured by medical assistants closest to the start of treatment as baseline, and at onset of every treatment cycle. Patients are weighed without shoes, in light clothes or hospital gowns, using a Seca digital scale with graduation 0.01 kg. Body height is measured to the nearest 0.1 cm with the same digital scale with graduation 0.1 cm.

Patients' demographics (age, sex, and ethnicity), and disease characteristics (left versus right colon cancer, RAS status) are collected. Other clinical variables considered to be important prognostic factors are collected and included in the analysis: TNM cancer stage, histological grade, peripheral blood neutrophil-lymphocyte ratio, serum carcinoembryonic antigen (CEA) level, ECOG performance status, Charlson comorbidity index.²⁵

(iii) Study design

Disease is staged by CT from thorax to pelvis or positron emission tomography-computed tomography (PET-CT). Clinical assessment (history taking and physical examination) and routine laboratory tests (complete blood counts, liver and renal function tests) are performed at baseline and before every treatment cycle according to daily practice. Adverse events are assessed using clinical and laboratory data, and graded by using Common Terminology Criteria for Adverse Effects, version 4.02.

The treatment doses and administration dates are recorded at chemotherapy infusion tables. Any treatment delay and dose reduction is recorded.

Patient is followed up at each treatment cycle. Some patients opt for treatment interruption after four to six months of treatment to avoid cumulative toxicity and preserve a good quality of life, and are put on close monitoring, treatment can be reinitiated when progression is detected. Interval assessments of disease response are made with physical examination (every clinic visit), serum CEA level, and three to six monthly CT, PET-CT or X-ray.

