We use Chi squared test to explore the association between weight change and dichotomous outcomes (dose reduction in treatment). Then separate regression models are used to further estimate the association as multivariate analyses. Weight change will be analysed as continuous variable, and ordinal variable (coding continuously 0, 1 and 2 for weight loss, stable weight and weight gain respectively). Dose reduction is analysed as dichotomous variable. The models will be adjusted for age, sex, targeted therapies. Other variables, such as Charlson's comorbidity index, and BMI can be included as covariables. Likelihood ratio test

will be used to compare models for selecting the final model. BMI has been found to be correlated positively with muscle mass, and is associated with treatment outcomes and side effects in different cancers.

Stata is used for all analyses. All significance tests are two-sided.

e) Existing Facilities:

The Department of Clinical Oncology at Tuen Mun Hospital will be the primary center for the conduct and analytic work in this study. We have an experienced team of researchers of performing cancer research.

f) Justification of Requirements:

Travel costs: We have included in our budget travelling costs for one trip to attend international conferences (\$10,000) in year 3. This is to reflect the need to present results at leading international conferences. This travel is mainly intended for international conference attendance.

Publication costs: These will cover the fee to publish the results in high-profile impact Open Access journals estimated at \$20,000 each. We will promote Open Access publications, according to the 2003 Berlin Declaration, as an additional mean to disseminate research effectively to large audiences. Publications will be uploaded to the open access repository "Dryad" and official site of Tuen Mun Hospital.

Other goods: scientific software: i) Stata-SE 15 one-core statistical software license for 1 computer (USD\$1,695 ~ HKD\$13,302). English editing services for research articles estimated at \$5,000 each. We further prepare \$3,000 for reference materials. We budget \$1,000 each year for stationeries and other expenses (e.g. printing and postage) because we expect printing and photocopying of a large amount of literature as well as miscellaneous office expenses relate mostly to the data collection, analysis, reporting and writing phase of the study.

g) Purpose and Potential:

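### The planned 240 patients do not follow from the stated inputs: they need about 78 to 97 patients for 80% power, and 240 would give over 99%.

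*Protocol*

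**What the plan says.** The sample size paragraph stands in the Protocol, section d) Plan of Investigation, (i) Subjects. It gives these inputs:

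- Exposed share: "Estimated proportion of subjects having significant weight loss is approximately 15" per cent.
- Effect: "Risk ratio of dose reduction was about 3.0 for patients with significant weight loss, according to a study in adjuvant setting".
- Rate in the unexposed: "Prior study indicated that the failure rate among controls is 0.2".
- Type I error 0.05. The section on data processing and analysis adds: "All significance tests are two-sided".
- Result: "We will need to recruit 240 patients to be able to reject the null hypothesis", with a power of 0.8 and with dose reduction named as primary.
- 10% loss to follow-up, which raises 240 to 264.

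The tool is G*Power and the planned test is logistic regression. The paragraph states no covariate R-squared, design effect or other inflation. The endpoint it powers is dose reduction, which the list of outcome measures in section c) places under "Secondary endpoints: Dose reduction is defined as <70% of relative dose intensity".

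**The concern.** Going from 20% to 60% is a very large difference. Even with only 15% of patients exposed, it should not take 240 patients to detect it with 80% power. If the printed inputs lead to a much smaller number, then the effect, the sample size and the power cannot all be as stated.

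This paragraph is the protocol's only justification for 240 (264 enrolled). As written, it tells the reader that the study has 80% power for a tripling of the risk of dose reduction. If 240 in fact gives 80% power for about a doubling, a null result would have to be read quite differently. The reader also cannot tell whether the planning assumption for the exposed group was 60% or something near 43%.

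**Working it through.** **Inputs, all from the Protocol.** Exposed share f = 0.15. Unexposed rate p0 = 0.20. Exposed rate p1 = 3.0 × 0.20 = 0.60. Two-sided alpha 0.05 (z = 1.960), power 0.80 (z = 0.8416). Overall rate P = 0.85 × 0.20 + 0.15 × 0.60 = 0.26. Odds ratio = (0.60/0.40)/(0.20/0.80) = 6.

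**Total N for 80% power on these inputs.**

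1. Two proportions, pooled variance under the null: N = [1.960 √(P(1−P)/(f(1−f))) + 0.8416 √(p1(1−p1)/f + p0(1−p0)/(1−f))]² / (p1−p0)². With the numbers: [1.960 × √(0.1924/0.1275) + 0.8416 × √(1.6 + 0.1882)]² / 0.16 = (2.408 + 1.125)² / 0.16 = **78.0**.
2. Logistic regression, Wald test on the log odds ratio: N = (1.960 + 0.8416)² × V / (ln 6)², with V = 1/(0.85 × 0.16) + 1/(0.15 × 0.24) = 35.13. This gives 7.849 × 35.13 / 3.210 = **85.9**.
3. Two proportions, unpooled: 7.849 × 1.788 / 0.16 = **87.7**.
4. Wald with the null variance V0 = 1/(0.1924 × 0.1275) = 40.77 in the alpha term: (1.960 × √40.77 + 0.8416 × √35.13)² / 3.210 = **95.4**.
5. Formula 1 with continuity correction: **96.6**.

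The stated 240 is not reproduced. It is about 2.5 (240/96.6) to 3.1 (240/78.0) times what the inputs require.

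**Power at N = 240 (36 exposed, 204 not), 60% versus 20%.** Pooled: (0.4 × √240 − 2.408)/1.337 = 2.83, so the power is 99.8%. Exact chi-square gives 99.8%; Wald and Fisher's exact test give 99.7%.

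**Can a reasonable variation in the inputs close the gap?**

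| Variation | Total N for 80% power |
|---|---|
| 10% exposed instead of 15% | 107–140 |
| Risk ratio 2.5 instead of 3.0 | 137–162 |
| Both together | 189 (pooled), 192 (Wald), 225 (continuity-corrected) |
| 0.2 read as the overall rate (0.2/1.3 = 15.4% versus 46.2%) | 117–146 |
| Power 0.90 or 0.95 (pooled) | 106 or 133 |

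With the other inputs as printed, covariate adjustment alone would need an R-squared of 1 − 85.9/240 = 0.64 (Wald) to 1 − 78.0/240 = 0.675 (pooled) to reach 240.

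**What would give 240?** If 3.0 is an odds ratio, p1 = 0.75/1.75 = 42.9%. The same five formulas then give 229 (pooled), 225 (Wald), 274 (unpooled), 266 (Wald with null variance) and 262 (continuity-corrected), and power at 240 is 79% to 82%. Other single changes also lead to 240: a control rate of about 0.08 to 0.09 with a risk ratio of 3.0, or about 4% to 5% exposed with 60% versus 20%. The protocol does not say which, if any, applies.

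**What 240 detects with 80% power** on a control rate of 0.20 and 15% exposed: 42.3% (pooled; risk ratio 2.12, odds ratio 2.93), 42.0% (Wald; 2.10, 2.90) or 43.2% (Fisher; 2.16, 3.05).

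**Loss to follow-up.** 240 × 1.10 = 264, but 264 × 0.90 = 237.6, so about 238 would remain evaluable. This is a minor point.

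**The case against.** The strongest reply is that little follows for the study. On the stated inputs it is larger than needed for dose reduction; if 3.0 was meant as an odds ratio, 240 is about right. The study is an observational pilot that adds no procedure or risk for patients, and neither recruitment nor analysis has to change. That is fair. It limits the point to a correction of the stated justification, but does not make the paragraph true.

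Second, two inputs are given as approximate. Moving both at once (10% exposed, risk ratio 2.5) brings N to 189–225, and an added covariate R-squared of 0.2 would lift the pooled figure to 189/0.8 = 236. Adjusted models are indeed planned. But this needs three departures from what is printed, and the paragraph states no R-squared.

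Third, 78 to 97 is the range of five formulas, not of all. A Wald test on the log risk ratio gives 60. That is further from 240 and is not the logistic analysis that the protocol names.

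Fourth, the cause cannot be settled from the document. That stands: the odds-ratio explanation is a possibility only, and any new wording must wait for the check of the calculation.

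Finally, calling dose reduction primary here and secondary in section c) is a separate inconsistency. It adds nothing to the arithmetic, but it bears on what the power statement covers.

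**Conclusion.** The concern holds. With the printed exposed share, control rate, risk ratio, alpha and power, the requirement is about 78 to 97 patients, and 240 gives about 99.7% to 99.8% power. The mismatch does not depend on the choice among the usual formulas, and the approximate wording of two inputs does not remove it. The conclusion assumes only that 0.2 is the rate in patients without significant weight loss, as the text says; reading it as the overall rate still leaves N at 117–146.

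The dose-reduction comparison is not underpowered on the stated inputs. What is wrong is the statement of what 240 patients can detect: about a doubling of risk with 80% power, not a tripling. The paragraph supports no statement about power for disease control rate or progression-free survival. This should be fixed; confidence in the arithmetic is high, while the origin of 240 remains unknown.

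**What to change.** Keep 240. Retrieve the G*Power input and the source of the 3.0, then restate the paragraph according to what they show:

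- If an odds ratio was used: odds ratio 3.0 (42.9% versus 20%), 15% exposed, two-sided alpha 0.05, power about 0.8 with 240 patients.
- If it is a risk ratio: risk ratio 3.0 (60% versus 20%), power above 0.99 with 240 patients; 240 patients give 80% power for a risk ratio of about 2.1.
- If another exposed share, control rate or a covariate R-squared was entered: print the value used.

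In the same paragraph, say that the power applies to dose reduction, listed as secondary in section c), and not to disease control rate or progression-free survival. State also that 264 enrolled with 10% loss leaves about 238 evaluable patients.

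The cost is one check of the calculation and its source and the rewording of one paragraph. No additional patients are needed and the recruitment target does not change.

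### The only power statement is attached to dose reduction, labelled primary there but secondary everywhere else, and its 80% does not follow from its own inputs

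*Protocol*

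**What the plan says.** The Protocol's abstract gives: "Primary outcomes: disease control rate, progression free survival. Secondary outcomes: Dose reduction of systemic chemotherapy". The main outcome measures at the end of section c) agree: "Primary endpoint: DCR which includes stable disease, partial response and complete response as defined in RECIST 1.1; and PFS", followed by "Secondary endpoints: Dose reduction is defined as <70% of relative dose intensity". Section d(iv), Data processing and analysis, keeps the same order, with DCR and PFS analysed under the primary outcomes and dose reduction under the secondary outcomes.

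The sample-size paragraph in section d(i) departs from this. The null hypothesis to be rejected there is that "the primary endpoints (incidence of dose reduction) for patient with and without significant weight loss are equal with probability (power) 0.8". Its inputs all concern dose reduction:

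- about 15% of patients with significant weight loss;
- for the size of the effect, "Risk ratio of dose reduction was about 3.0 for patients with significant weight loss, according to a study in adjuvant setting";
- for the comparison group without weight loss, "Prior study indicated that the failure rate among controls is 0.2";
- type I error 0.05.

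The result is 240 patients, raised to 264 for 10% loss to follow-up. The paragraph closes with "We will use logistic regression to evaluate this null hypothesis". Section d(iv) adds that all tests are two-sided. The Protocol gives no assumed DCR, hazard ratio, event count, power or detectable effect for DCR or PFS.

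**The concern.** There are two faults in one sentence, and correcting one does not remove the other.

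First, the label. Someone who reads the sample-size paragraph for the study's power will take 80% to apply to the primary endpoints. It applies to dose reduction, which three other parts of the Protocol call secondary. No effect on DCR or PFS is named that the study was planned to detect. Their results can still be read from confidence intervals, but a null result on either could not be set against any planned effect.

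Second, the arithmetic. Tripling a rate of 0.2 gives 0.6, a very large difference, and 240 patients look far too many for 80% power to detect it. If so, the stated ratio, the stated power or the stated number is wrong.

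**Working it through.** **Inputs (Protocol, section d(i); two-sided testing from d(iv)).** Weight-loss fraction 0.15, so 0.15 × 240 = 36 patients with and 204 without weight loss. Control rate p0 = 0.20. Ratio 3.0. Two-sided alpha 0.05, so z = 1.960.

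**Formula.** Two proportions with pooled variance under the null:

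power = Φ[(|p1 − p0| − 1.960 × s0) / s1], where

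- s0 = √[p̄(1 − p̄)(1/36 + 1/204)], with p̄ = 0.15 p1 + 0.85 p0
- s1 = √[p1(1 − p1)/36 + p0(1 − p0)/204]

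**1. As written, 3.0 a risk ratio.** p1 = 3.0 × 0.20 = 0.60 and p̄ = 0.26. Then s0 = 0.0793 and s1 = 0.0863. Power = Φ[(0.40 − 0.1554)/0.0863] = Φ(2.83) = 0.998. Solving for 80% power gives a total of 79. The stated 240 at power 0.8 is not reproduced.

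**2. 3.0 as an odds ratio.** The odds are 3.0 × 0.20/0.80 = 0.75, so p1 = 0.75/1.75 = 0.429 and p̄ = 0.234. Then s0 = 0.0766 and s1 = 0.0871. Power = Φ[(0.2286 − 0.1501)/0.0871] = Φ(0.90) = 0.816. Solving for 80% gives a total of 230. This comes close to the stated figure.

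**3. The planned test.** For a Wald test of the log odds ratio, SE = √[1/(36 p1(1 − p1)) + 1/(204 p0(1 − p0))].

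- 0.60 vs 0.20: ln 6.0 = 1.792, SE 0.383, power Φ(4.68 − 1.96) = 0.997.
- 0.429 vs 0.20: ln 3.0 = 1.099, SE 0.380, power Φ(2.89 − 1.96) = 0.825.

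**4. Other variants at 0.60 vs 0.20.** Continuity correction needs 98 patients, logistic-regression formulas 78 to 95, Fisher's exact test about 90. Reading 0.2 as the overall rate rather than the control rate needs 118, or 142 with continuity correction. None approaches 240.

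**5. Loss to follow-up.** 264 × 0.9 = 237.6. Power there is 0.998 (risk ratio) or 0.813 (odds ratio), so the loss adjustment does not explain the gap.

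**6. What 240 does detect with 80% power.** 0.423 vs 0.20, that is a risk ratio of 2.12 or an odds ratio of 2.93.

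**7. DCR and PFS, illustration only.** The Protocol gives no planning values, so these are assumed: 36 vs 204 patients, 80% power, loss versus no loss. DCR uses the formula above. PFS uses Schoenfeld's formula, HR = exp[(z + 0.8416)/√(events × 0.15 × 0.85)].

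| Endpoint, assumed value | Detectable, alpha 0.05 | Detectable, alpha 0.025 |
|---|---|---|
| DCR 90% without weight loss | fall of 18.4 points | 20.3 points |
| DCR 80% | 22.3 points | 24.6 points |
| DCR 70% | 24.2 points | 26.7 points |
| PFS, 150 events | HR 1.90 | HR 2.02 |
| PFS, 200 events | HR 1.74 | HR 1.84 |
| PFS, 240 events | HR 1.66 | HR 1.75 |

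The last row is the extreme case in which every one of 240 patients has an event. These figures do not describe the three-group log-rank test or the joint model planned in d(iv).

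**The case against.** The strongest reply is that this is a wording slip with little consequence. The phrase names dose reduction in its own parenthesis, and every input around it concerns dose reduction, so the Protocol never expressly claims power for DCR or PFS. The arithmetic gap probably turns on one word: logistic regression estimates an odds ratio, and on that reading power at 240 is about 82%. On the literal reading the study is larger than dose reduction needs. It is also a single-centre observational pilot, and sizing it on a secondary endpoint for which earlier data exist is permissible.

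Much of this stands. The direction is safe for dose reduction on the literal reading and about neutral on the other. Sizing on a secondary endpoint is acceptable if the Protocol says so. The odds-ratio reading is plausible, but the text does not establish it. The objection does not remove either fault. A pilot that states a hypothesis test, a type I error and a power should attach them to the right endpoint and make them agree. Nor does a safe direction for dose reduction tell the reader anything about DCR or PFS.

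It is also fair that detectable effects for DCR and PFS rest on assumed values, and that a two-group calculation treats weight loss as fixed although d(iv) defines it by the maximum change during treatment. Hence the table above is illustration only, and the values in the Protocol should be the sponsor's own.

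**Conclusion.** Wrong as written; to be corrected. The label in the sample-size paragraph contradicts the abstract, the endpoint list and the analysis section. The Protocol's only power statement therefore concerns a secondary endpoint.

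That 240 patients are needed for 80% power does not follow from a risk ratio of 3.0. On the stated inputs 240 is about three times the number needed (240/79 = 3.0). The discrepancy nearly closes if 3.0 is an odds ratio. The conclusion rests only on the Protocol's own inputs and holds across the standard test variants and the loss adjustment.

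It is not shown that DCR or PFS is underpowered. That cannot be judged, because the Protocol gives no planning values for them.

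**What to change.** Keep the sample size, the endpoints and the tests.

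1. In the sample-size paragraph, call the incidence of dose reduction the secondary endpoint, in line with the rest of the Protocol. If the sponsor did intend it as primary, the abstract, endpoint list and analysis section must be changed instead.
2. State whether 3.0 is a risk ratio or an odds ratio, and give the matching power at 240: about 99.8% or about 82%.
3. Add, with the sponsor's own values in the brackets: *The sample size was not calculated for DCR or PFS. With an assumed DCR of [x] without weight loss, [y] PFS events and alpha of [z] per primary endpoint, the effects detectable with 80% power at this sample size are [ ] for DCR and [ ] for PFS. This simple loss versus no-loss calculation does not describe the three-group log-rank test or the joint model.* DCR and PFS remain the primary tested endpoints and are reported with 95% confidence intervals.

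The cost is wording in one paragraph and one short calculation. The Protocol also gives up the appearance of 80% power for its primary endpoints, which its calculation never supported.

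### The sample-size figures of 240 needed, 10% loss and 264 in total do not agree: 264 preserves 240 patients only if loss is at most 9.1%

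*Protocol*

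**What the plan says.** The figures stand in the Protocol, section d) Plan of Investigation, (i) Subjects, under the sample size calculation. The base number is given as: "We will need to recruit 240 patients to be able to reject the null hypothesis" that the incidences of dose reduction with and without significant weight loss "are equal with probability (power) 0.8". The allowance follows: "Assuming 10% loss to follow-up, total number of patients to require is 264". The type I error is 0.05, and section d)(iv) adds that "All significance tests are two-sided".

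The inputs behind 240 are a share of about 15% with significant weight loss, an effect described as "Risk ratio of dose reduction was about 3.0 for patients with significant weight loss", and a comparison rate: "Prior study indicated that the failure rate among controls is 0.2". The planned test is logistic regression. No formula is given for the allowance, and no other section restates or reconciles 240, 10% and 264.

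**The concern.** A loss rate applies to the patients who are enrolled. To have n left after a proportion d is lost, the enrolled number N must satisfy N x (1 - d) >= n, so N = n/(1 - d). Adding d x n to n gives a smaller number, and the enrolled cohort then falls short of n at the very loss rate that was assumed.

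What is at stake is the consistency of the recruitment target. A reader who takes the text at face value will believe that 264 enrolled patients with 10% lost leave the required 240, and they do not. The same step would also give too small a total if it were repeated on a different base number.

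**Working it through.** **Inputs**, all from the Protocol, section d)(i): n = 240, d = 0.10, stated total 264.

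**Reproducing the stated total.** n x (1 + d) = 240 x 1.10 = 264, an exact match. The allowance was therefore evidently taken as 10% of the number to be kept (24 patients).

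**What 264 delivers at 10% loss.** 264 x 0.90 = 237.6, which is 2.4 below 240.

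**The loss that 264 can absorb.** 1 - 240/264 = 24/264 = 9.1%.

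**Total that keeps 240 at 10% loss.** n/(1 - d) = 240/0.90 = 266.7, so 267. Check: 267 x 0.90 = 240.3, while 266 x 0.90 = 239.4 is too few.

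**Gap.** 267 - 264 = 3 patients, and 3/264 = 1.1%.

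**Does the gap cost power?** That depends on what 240 delivers, so the base was checked on the stated inputs: control rate 0.20, risk ratio 3.0 (hence 0.20 x 3.0 = 0.60), a 15:85 split, two-sided 0.05, power 0.80. For a binary covariate with prevalence B in logistic regression, Hsieh's formula is

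N = [z(0.975) x sqrt(P(1 - P)/B) + z(0.80) x sqrt(p1(1 - p1) + p2(1 - p2)(1 - B)/B)]^2 / [(p1 - p2)^2 x (1 - B)]

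with p1 = 0.20, p2 = 0.60, B = 0.15 and P = 0.85 x 0.20 + 0.15 x 0.60 = 0.26.

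- First term: 1.960 x sqrt(0.1924/0.15) = 2.220.
- Second term: 0.842 x sqrt(0.16 + 0.24 x 0.85/0.15) = 0.842 x sqrt(1.52) = 1.038.
- N = (2.220 + 1.038)^2 / (0.16 x 0.85) = about 78.

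Other methods, and the alternative reading of 3.0 as an odds ratio (odds 0.25 x 3 = 0.75, rate 0.75/1.75 = 0.429), give:

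| Method | Total N, 0.20 v 0.60 | Total N, 0.20 v 0.429 |
|---|---|---|
| Two proportions, no continuity correction | 79 | 230 |
| Two proportions, continuity correction | 98 | 264 |
| Hsieh, logistic | 78 | 230 |
| Demidenko, logistic | 86 to 95 | 225 to 266 |

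At 0.20 v 0.60, normal-approximation power is above 99% at both 237 and 240. At 0.20 v 0.429 it is about 0.82 at 240 and 0.81 at 237.6; with Fisher's exact test it is about 0.79 at 240.

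If 240 is simply assumed to give exactly 80% power (control rate 0.20 and a risk ratio of about 2.12), then 237.6 gives 79.6%. The Protocol does not state that effect size.

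**The case against.** The strongest reply is that the gap is immaterial. Three patients is 1.1% of the target in a pilot observational study whose inputs are approximate (15% and 3.0) and whose loss rate is a round 10%. The Protocol reports more than 150 new first-line patients a year and recruits for 24 months, so over 300 may be available before eligibility is applied, and either total is within reach. All of that stands, and it makes this a minor point. It does not make the three figures agree.

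A second reply is that the text speaks of recruiting 240 and never calls them evaluable. That is true, but if 240 were already the enrolled number there would be no reason to add an allowance. Reading 240 as the number to remain is the only reading under which the addition makes sense.

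A third reply is that lost patients may still contribute. Under the definition of PFS they are censored, and for dose reduction the doses and administration dates are recorded as treatment is given, so some lost patients may have usable data. This stands: about 237 is what remains if lost patients give no dose-reduction data, and the Protocol does not say that they give none.

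A reader might also infer that the study is left underpowered, at 79.6% instead of 80%. The Protocol does not support that. On its stated risk ratio and control rate, 237 patients give over 99% power. On the odds-ratio reading, the uncorrected calculation still gives about 81%. Where power is below 80% under that reading (Fisher's test), it is already so at 240, so the base number is responsible and not the allowance.

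**Conclusion.** The point holds as a small arithmetic inconsistency. The total of 264 does not leave 240 patients after 10% loss. It leaves about 237, or it covers a loss of at most 9.1%. The difference from the total obtained by division is 3 patients (1.1%). This rests on two assumptions: that the 10% refers to enrolled patients, and that 240 is the number meant to remain. The figure of about 237 also assumes that lost patients give no dose-reduction data.

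No loss of power follows. The 79.6% is hypothetical and applies only if 240 gave exactly 80% power, which the stated inputs do not bear out. Nor does it follow that the target must be raised to 267. That number would lend precision to a base of 240 that does not follow from the stated risk ratio of 3.0 and control rate of 0.2, and it would lapse as soon as the base was revised.

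**What to change.** Keep 264 and replace the allowance statement with one that is true of it: a total of 264 allows for about 9% loss to follow-up, and at 10% loss about 237 patients would be evaluable if those lost give no dose-reduction data. If the base of 240 is revised when it is reconciled with the stated risk ratio and control rate, compute the new total as n/(1 - loss), rounded up, and show the formula. The cost is one sentence, with no extra patients and no change to procedures.
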